Overview of the Design: We propose a two-arm RCT: participants will be randomized to (a) smartphone-based MBSR app (Headspace) or (b) active control (breathing app) for 14 days. Loneliness and quality of social interactions will be assessed using end-of-day diary surveys at baseline (T1) and 14-days after randomization (T2).

Specific Aims and Hypotheses:

Aim 1. *To examine the feasibility and acceptability of providing a mobile health mindfulness meditation training intervention to caregivers with significant caregiving stress and loneliness.*

H1a-b: We expect 80% of caregivers screened will report willingness to use the mindfulness app and at least 75% of participants will complete mindfulness training (at least 80% of expected engagements with the app).

Aim 2. *To examine whether a mobile health mindfulness meditation training intervention reduces loneliness and improves quality of social interactions.*

H2a-b: Participants randomized to mindfulness will demonstrate greater improvements (vs. control) in loneliness (3-item UCLA Loneliness Scale) and quality of social interactions (level of intimacy, involvement and enjoyment during/immediately following a social interaction) via end-of-day diary surveys on REDCap.

Aim 3. *To examine mechanisms whereby mindfulness meditation training reduces loneliness and improves quality of social interactions.*

H3a-b. Participants randomized to mindfulness will demonstrate greater improvements (vs. control) in the mindfulness skills of acceptance through nonjudgment and non-reactivity (Five-Facet Mindfulness Questionnaire [FFMQ]), emotion regulation (Difficulties in Emotion Regulation Scale [DERS]), and self-compassion (Self-Compassion Scale) at follow-up.

H3c (exploratory): Effects of mindfulness skills on loneliness and quality of social interactions will be mediated by improvements in emotion regulation.

II. CHARACTERISTICS OF THE RESEARCH POPULATION

- A. Number of subjects.** We propose a sample size of 50 older adults, enrolling a total of 63 participants over 13 months, using a 20% attrition rate for enrollment estimates.

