- E. Randomization.** The Center statistician will be responsible for randomizing all participants. To ensure treatment balance, new participants will be sequentially assigned to receive (a) smartphone-based MBSR app (Headspace) or (b) active control (breathing app) using covariate adaptive randomization, which will take into account covariates (i.e., age and gender) and previous assignment of participants. The statistician will then inform the project coordinator of study condition. In all instances, members of the research team responsible for data collection will remain blind to study condition and the statistician will be the only one with access to the randomization schedule.
- F. Assessments.** Data obtained during the assessments will be obtained specifically for research purposes. Participants will complete the standard STAR baseline and follow-up assessments, with the addition of mindfulness (using the Five-Facet Mindfulness Questionnaire [FFMQ]), emotion regulation (using the Difficulties in Emotion Regulation Scale [DERS]), and Self-Compassion Scale

questionnaires. Loneliness (using the 3-item UCLA Loneliness Scale) and quality of social interactions will be assessed daily using end-of-day diary surveys and all baseline measures will be repeated 3 days after the 14-day intervention.

1. Initial eligibility phone screen: verbal informed consent will be conducted; demographics data will be collected (age, gender, race/ethnicity, education, marital status, living arrangements, caregiver status); and screening instruments will be administered (4-item Perceived Stress Scale, cognitive assessment [Telephone Interview for Cognitive Status; TICS], AUDIT-C, and UCLA Loneliness 3-item scale). Those who do not endorse exclusion criteria for cognition and alcohol abuse will be invited for an initial assessment for further assessment for participation in the study.

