3. End-of-day diary surveys via REDCap: Subjects will complete end-of-day dairy surveys for 3 days pre-intervention and 3 days post-intervention. The diaries will be completed in REDCap and will ask about subjective experience of loneliness (using the 3-item UCLA Loneliness Scale) and quality of social interactions.
4. Follow-up assessments: 3-days after the 14-day intervention, participants will complete assessment measures from the baseline interview and an evaluation regarding their experience of the study via telephone or Zoom with a Clinical Research Coordinator.

G. Description of Interventions

Mindfulness Intervention. Participants randomized to the mindfulness intervention will complete up to 14 days of an individual mobile health mindfulness-based intervention training (dose based on a recent study of smartphone-based mindfulness training that demonstrated efficacy in reducing loneliness). Participants will be allotted up to 2 weeks to complete all sessions. The mindfulness intervention will be delivered via Headspace, a mindfulness-based smartphone app. Subjects will be instructed to engage with the app's first 10 introductory sessions. These sessions are intended to act as a general introduction to mindfulness meditation and incorporate techniques such as breath awareness and body scanning. Each session will be completed daily, has a duration of approximately 10 minutes, and is guided by a former Buddhist monk. Upon completion of the introductory sessions, additional content for the four final sessions will be accessible, including sessions from the Reframing Loneliness course, which teaches on connectivity, and the Kindness course, which teaches compassion toward self and others. Note: The study team is not evaluating the safety or effectiveness of the app, nor is the app FDA approved.

Breathing Control. Participants randomized to the breathing app control intervention will complete up to 14 days of an individual breathing app. Participants will be allotted up to 2 weeks to complete all sessions. The breathing control intervention will be delivered via Headspace. The intervention is designed to be structurally equivalent to the mindfulness-based study intervention on key common

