Participants will be characterized at baseline with regards to demographic characteristics, degree of social disconnectedness, caregiver distress, well-being (depressive symptoms, quality of life), cognitive function, and relationship satisfaction with the person they care for. A baseline check of randomness will be conducted for each demographic and outcome variable collected. Mixed-effect linear models (MLMs) will focus on time × condition interactions using end-of-day diary surveys and baseline to follow-up data.

Aim 1. To examine the feasibility and acceptability of providing a mobile health mindfulness meditation training intervention to caregivers with significant caregiving stress and loneliness.

H1a-b: We expect 80% of caregivers screened will report willingness to use the mindfulness app and at least 75% of participants will complete mindfulness training(at least 80% of expected engagements with the app).To assess hypothesis 1, the number of subjects and the number of sessions completed by each will be examined to determine if at least 80% of subjects engage with the app and at least 75% complete a full dose of the intervention.

Aim 2. To examine whether a mobile health mindfulness meditation training intervention reduces loneliness and improves quality of social interactions.

H2a-b: Participants randomized to mindfulness will demonstrate greater improvements (vs. control) in loneliness (3-item UCLA Loneliness Scale) and quality of social interactions (level of intimacy, involvement

and enjoyment during/immediately following a social interaction) via end-of-day diary surveys following procedures by Mote et al.²⁹ To assess hypothesis 2, multilevel mixed-effect linear models (MLMs) will focus on time × condition interactions in end-of-day survey-sampled loneliness and quality of social interactions outcomes (using all available data).

Aim 3. To examine mechanisms whereby mindfulness meditation training reduces loneliness and improves quality of social interactions. H3a-b. Participants randomized to mindfulness will demonstrate greater improvements (vs. control) in the mindfulness skills of acceptance through nonjudgment and non-reactivity (Five-Facet Mindfulness Questionnaire [FFMQ]), emotion regulation (Difficulties in Emotion Regulation Scale [DERS]), and Self-Compassion Scale at follow-up.

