H3c (exploratory): Effects of mindfulness skills on loneliness and quality of social interactions will be mediated by improvements in emotion regulation. To assess hypothesis 3a-b, multilevel mixed-effect linear models (MLMs) will focus on time × condition interactions in mindfulness skills and emotion regulation at follow-up. Exploratory hypothesis 3c examines our belief that the effects of the mindfulness meditation training on loneliness and quality of social interactions are not only direct, but are also indirect, working through emotion regulation. To assess exploratory hypothesis 3c, we will use two simple path analyses using multiple regression, one assessing the link from intervention to emotion regulation to loneliness, and one assessing the link from intervention to emotion regulation quality of social interactions.

V. DATA SAFETY AND DATA MONITORING PLAN

A. Data and Safety Monitoring Plan. The purpose of the Data and Safety Monitoring Plan (DSMP) is to specify the procedures and rationales of the current study to ensure the safety of participants and the validity and integrity of the data. This specifies who will look at the data and review any adverse events, how often, and what they are authorized to do. The use of Data and Safety Monitoring Boards (DSMBs) may be indicated if studies have multiple clinical sites, are blinded (masked), and/or employ particularly high-risk interventions or vulnerable populations. This study on the other hand will be conducted utilizing a low risk intervention in a population of older adults residing independently in the community. Therefore, we have chosen to include a *Data Safety Monitoring Plan Committee* that, while constituted by individuals connected to the study/STAR Center, will systematize monitoring safety issues throughout its duration. The Committee will be led by a designated Safety Officer (SO).

The Principal Investigator (PI) will be responsible for ensuring participants' safety on a daily basis. The DSMP Committee will act in an advisory capacity to the NIA Director and to evaluate the progress of the study, including periodic assessments of data quality and timeliness, participant recruitment, accrual and retention, participant risk versus benefit, performance of trial sites, and other factors that can affect study outcome. The committee will make recommendations to NIA's Director concerning the continuation, modification, or conclusion of the trial.

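### Allocation balances age and gender but no Aim 2 or Aim 3 model names them: a mild precision loss if they predict change, and a separate confounding risk on the exploratory H3c path

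*Combined protocol and SAP*

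**What the plan says.** Section III.E assigns participants sequentially "using covariate adaptive randomization, which will take into account covariates (i.e., age and gender) and previous assignment of participants". Section II.A plans for 50 participants, "enrolling a total of 63 participants over 13 months, using a 20% attrition rate for enrollment estimates". Both factors are recorded at the phone screen (III.F, item 1): "demographics data will be collected (age, gender, race/ethnicity, education, marital status, living arrangements, caregiver status".

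The analyses are in section IV:

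- **Aim 2:** "multilevel mixed-effect linear models (MLMs) will focus on time × condition interactions in end-of-day survey-sampled loneliness" and in social-interaction quality. The diary data behind it come from III.F, item 3: "Subjects will complete end-of-day dairy surveys for 3 days pre-intervention and 3 days post-intervention".
- **Aim 3, H3a-b:** "multilevel mixed-effect linear models (MLMs) will focus on time × condition interactions in mindfulness skills and emotion regulation at follow-up".
- **Aim 3, H3c (exploratory):** "we will use two simple path analyses using multiple regression, one assessing the link from intervention to emotion regulation to loneliness", and a second one for social-interaction quality. The stated belief is that the training effects "are not only direct, but are also indirect, working through emotion regulation".

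No covariate is named for any of these, and none is ruled out. In section IV, demographics appear only in the baseline description and in a check of baseline comparability. The random effects of the diary models, the coding of age in the allocation algorithm, and whether H3c uses follow-up or change scores are not stated.

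**The concern.** Two separate issues arise.

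**Precision.** Balancing on a factor that predicts the analysed quantity makes the arm difference less variable. A model that omits the factor still counts its variation in the standard error, so the error is overstated and the test rejects too rarely. A time × condition contrast uses each person as their own control, so an effect of age or gender on the level of a score cancels. Only an effect on change matters. With about 50 completers, lost precision is worth recovering if recovery is cheap.

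**H3c.** Emotion regulation is not randomised. If age or gender drives both emotion regulation and the outcome, the regression of one on the other shows an association with no causal path behind it. Balanced arms do not prevent this. A mechanism reported from a pilot could then misdirect later work.

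**Working it through.** **Plan's own figure.** 50 / (1 − 0.20) = 62.5, rounded up to 63. This reproduces. No alpha, power, effect size, SD or covariate association is given, so no power figure can be reproduced and everything below is conditional.

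**Inputs from the protocol.** 63 allocated and 50 retained (II.A); 67% women (target in II.B); 3 + 3 diary days (III.F).

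**Assumptions.** 1:1 allocation; two-sided 5%; minimisation with a biased coin of 0.8; age split 50/50; the two factors contributing equally; dropout at random; R² = share of variance explained, 0–30%.

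**Step 1: formula for person-level change, perfect balance, 25 per arm.** Model SE / true SE = 1/√(1 − R²). Actual size = 2[1 − Φ(1.96/√(1 − R²))]. At 0.8 SD, 0.8/√(2/25) = 2.828; unadjusted power = Φ((2.828 − 1.96)/√(1 − R²)) and adjusted power = Φ(2.828/√(1 − R²) − 1.96).

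| R² on change | 5% | 10% | 20% | 30% |
|---|---|---|---|---|
| SE ratio | 1.026 | 1.054 | 1.118 | 1.195 |
| Actual size | 4.4% | 3.9% | 2.8% | 1.9% |
| Power, unadjusted | 81.4% | 82.0% | 83.4% | 85.0% |
| Power, adjusted | 82.7% | 84.6% | 88.5% | 92.2% |

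**Step 2: simulation with imperfect balance** (40,000 runs per cell; Monte Carlo SE 0.11 point at 5%).

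| R² on change | 0% | 5% | 10% | 20% | 30% |
|---|---|---|---|---|---|
| Type I error, unadjusted (%) | 4.9 | 4.8 | 4.4 | 3.5 | 2.7 |
| Power change from adjustment, 0.8 SD (points) | −0.5 | +0.9 | +2.5 | +6.1 | +9.2 |
| Power change, 0.5 SD (points) | −0.5 | +1.3 | +3.4 | +7.9 | +14.2 |
| Power change under simple randomisation, 0.8 SD (points) | −2.0 | +0.1 | +2.5 | +6.5 | +10.7 |

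Adjusted type I error is 4.9–5.2% throughout. Repeat runs gave unadjusted error of 4.5–4.8, 4.1–4.4, 3.4–3.5 and 2.7–2.8% at 5, 10, 20 and 30%. The last row shows that most of the gain would arise without any balancing.

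**Step 3: level versus change.** With 30% of level and none of change explained, the change test had a model SE of 0.281 against an empirical 0.280, and size 4.7%. Nothing is lost.

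**Step 4: diary models.** Step 2 applies to the Aim 3 pre/post scores and to a diary model with a random person slope. In a random-intercept-only diary model with no other person-level differences in change, unadjusted size is 5.0/5.1/5.1/5.2/5.5% at 0/5/10/20/30% and adjustment at 0.8 SD is worth −0.5 to +2.2 points. If people truly differ in change, that model errs the other way. In one simulated setting its SE was 0.163 against an empirical 0.249. With a true person slope at 25% or 50% of the remaining contrast variance, its type I error is about 8% or 13%, with or without the covariates.

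**Step 5: which terms matter.** In one complete data set fitted by REML with a random slope, the time × condition SE was 0.2670. It was unchanged (within 0.0001) with age and gender as main effects, and 0.2169 with their time interactions.

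**Step 6: H3c path, true effect zero.** If the factors explain R²_M of emotion regulation and R²_Y of the outcome in the same direction, the unadjusted coefficient is biased by √(R²_M × R²_Y) = r in SD units. With 50 − 3 = 47 degrees of freedom, the test statistic shifts by r√47/√(1 − r²). For r = 0.10 this is 0.10 × 6.856/0.995 = 0.689, and Φ(0.689 − 1.96) + Φ(−0.689 − 1.96) = 10.6%.

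| R² in both scores | 0% | 5% | 10% | 20% | 30% |
|---|---|---|---|---|---|
| Rejection, formula (%) | 5.0 | 6.4 | 10.6 | 28.8 | 57.8 |
| Rejection, simulated (%) | 4.9 | 6.4 | 10.7 | 29.0 | 57.4 |
| Follow-up scores plus both baselines (%) | 5.0 | 5.0 | 5.6 | 6.5 | 7.6 |

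With age and gender entered, rejection is 4.9–5.1%. The last row omits age and gender and assumes that half of the unexplained variance in each score is shared between pre and post. With change scores and level-only effects, or with age and gender effects that cancel, there is no inflation (4.0–5.2%). The path from intervention to emotion regulation is unbiased (0.50 against a true 0.50).

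**The case against.** The best counter-case has four parts, and much of it stands.

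- **Change, not level.** Baseline and follow-up are under three weeks apart, and nothing in the protocol suggests that age or gender predicts change over that interval. This stands. The precision point is conditional, and at 5% explained it is small.
- **Aim 2 depends more on the random effects.** This also stands: naming age and gender does not repair a diary model that ignores person-level differences in change. The fix therefore includes that term.
- **General advice.** Most of the power gain is what any predictive covariate would give. True, but the allocation already treats these two factors as important, and they are collected in any case.
- **H3c is exploratory and open to many confounders.** Baseline loneliness, depressive symptoms and burden are other possible common causes. H3c also speaks of improvements in emotion regulation, which may point to change scores. Both are fair, but the score is not specified, so the exposed version is not ruled out.

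A reader might infer more than this. The protocol does not show that age or gender predicts any of these scores, so the 29% and 57% false-positive rates for H3c are the far end of an assumed range. It does not say that dropout will depend on age in one arm, so a biased treatment contrast cannot be claimed on that ground. It does not say that the baseline comparability check will be used to choose covariates. And naming no covariate is not the same as excluding one.

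**Conclusion.** The point holds as a modest matter of prespecification. Allocation uses age and gender and no Aim 2 or Aim 3 model names them. The tempting conclusion that standard errors are too wide whenever these factors predict the scores is not supported: they must predict person-level change, and the direction for Aim 2 depends on random effects that the plan leaves open.

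Where it applies, the effect is conservative: small at 5–10% of change variance explained, appreciable only at 20–30%, and without bias in the randomised contrast. The H3c risk is a different matter and does not come from the balancing. It needs age or gender to predict both analysed scores without cancelling, and it largely disappears with both baseline scores in the model, or with change scores when the effects are on level only.

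Confidence is medium. The omission is plain from the text, but every size rests on the assumptions listed with the calculations.

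**What to change.** - **Aim 2 and Aim 3 mixed models:** prespecify age and gender, in the form used by the allocation algorithm, as age × time and gender × time together with their main effects. Main effects alone change nothing with complete data.
- **Diary models:** state the random effects and include a random person-level change term.
- **H3c:** state which scores are analysed. Enter age, gender and the baseline emotion-regulation and outcome scores in both regressions of each path analysis. Say in the plan that this does not remove confounding by other common causes.

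The cost is wording, about 2 degrees of freedom for the contrast, and about 0.5 point of power at 0.8 SD if the factors explain nothing. No new data are needed.

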- B. Gender of subjects.** Women will be well-represented in this study. Caregivers in the US are more likely to be women (67%); Caregivers are also more likely to be white, non-Hispanic (67%), while 10% are African American and 8% are Hispanic. Using the 2018 Alzheimer's Disease Facts and Figures along with our local demographic distributions, we plan to target 25% minority and 67% women enrollment. We will use the extensive resources in place to meet our minority recruitment goals (including targeting men for enrollment, as they represent the gender minority in the caregiver population).
- C. Age of subjects.** All subjects will be 50 years of age or older.
- D. Racial and ethnic origin.** Subjects will represent the demographics of the local population of subjects at the community organization, as shown in the following table:

Racial Categories	Female	Male	Female	Male	
American Indian/Alaska Native	0	0	0	0	0
Asian	2	1	0	0	3
Native Hawaiian or Other Pacific Islander	0	0	0	0	0
Black or African American	4	2	1	1	8
White	30	14	2	1	47
More than One Race	2	1	1	1	5
Total	38	18	4	3	63

E. Inclusion Criteria (assessed at the HARP screening assessment)

1. Age \geq 50 years old.
2. English speaking.
3. Caregiver for a community-dwelling family member with ADRD, living with (or in close proximity to) family member with dementia.
4. Elevated caregiving distress: above population mean (>11) on 10-item Perceived Stress Scale (PSS-10) and/or at least moderate caregiver strain (score ≥ 5) on the Modified Caregiver Strain Index (MCSI).
5. Social disconnectedness: UCLA Loneliness Scale: Short Form score of ≥ 5 .
6. Access to e-mail in order to complete the e-consent module in REDCap which will be used in this study.

F. Exclusion Criteria (assessed at the HARP screening assessment)

1. Non-English speaking because our primary community partner agency (Lifespan) cannot currently accommodate non-English speaking clients.
2. Those with significant cognitive impairment on a cognitive screening measure at the HARP screening assessment.
3. In order to test the effects of developing mindfulness skills in a novice population, those with a regular systematic mindfulness meditation or related mind-body practice (>2 times per week) will be excluded.

G. Vulnerable Subjects.

Individuals who are 50 years of age and older with social risk factors for poor mental and physical health outcomes will be included. The results of this study will inform

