future research and clinical interventions aimed at improving mental health treatment for older caregivers.

III. METHODS AND PROCEDURES

A. Design. This study is a two-arm RCT: participants will be randomized to (a) smartphone-based MBSR app (Headspace) or (b) active control (breathing app) for 14 days. Loneliness and quality of social interactions will be assessed using end-of-day diary surveys at baseline (T1) and 14-days after randomization (T2).

The study team will remain vigilant about any further changes that need to be made to study procedures if there are changes to the research reboot guidance found here: <https://www.urmc.rochester.edu/coronavirus/coronavirus-research/guidance-for-researchers/human-subjectsresearch.aspx>

B. Recruitment. Subjects will be recruited via the IRB approved HARP Population Study (RSRB00068059), a research registry run by the current study's Investigators. In compliance with procedures of the Population Study protocol, subjects of the Population Study consent to allow HARP Population Study researchers to share subjects' identifiable data (both name and contact information) with investigators conducting HARP research at the University of Rochester; in addition, they consent to allow their data collected as part of the Population Study to be included in their research record for subsequent HARP studies they participate in, including the current study. All eligible participants will be given information about this study at their HARP phone screen assessment. Contact information is collected and maintained via the IRB approved HARP Database Study. A brochure describing the study will be given to participants in the HARP Population study (brochure is uploaded in the RSRB online application). Information about the study will also be posted on the webpage of a community organization for older adults, www.beyondthenest.com (content to be displayed is uploaded in the RSRB online application) and the URMC Clinical Trials website. Information about this study will also be provided in the ResearchMatch registry. RSRB-approved study brochures describing the study will be posted at clinics and community organizations serving older adults.

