C. Screening. We will utilize a REDCap eligibility screening survey given the relatively low base rate of loneliness, which is our key inclusion criteria, to increase the efficiency of our screening/enrollment process. Information about the study will be provided at the beginning of the survey. Individuals who complete this survey and endorse loneliness (UCLA Loneliness Scale) and at least mild stress will have the option to provide their contact information to share with the Healthy Aging Research Program (HARP) staff to complete the HARP Database (RSRB00067245) and Population Study (RSRB00068059) assessments, which will provide information needed to determine final eligibility for this Mindfulness study, which is part of the Rochester Roybal Center for Social Ties & Aging Research. The link to the eligibility screen will be available via ResearchMatch, the URMC Clinical Trials website, and the URMC website with information about the study.

D. Process of Consent. Eligible participants who are scheduled for a baseline interview (after phone screening) will provide informed consent prior to start of the interview. Consent will be done via telephone or Zoom. E-consent will be done through the REDCap module. An agreed upon security question will be used for the subject to access the E-consent. The informed consent process will be conducted in a manner to facilitate questions from potential study subjects. If a study team member is unable to answer a question, an investigator will be contacted. All questions from potential subjects should be answered prior to signature. Subjects will certify that the information

in the document is correct (which includes their name), and that electronically signing is the equivalent of signing a physical document. Subjects will sign using finger, mouse or stylus. The study coordinator's name and timestamp will be saved in REDCap as their signature. Consents will be stored within REDCap, and a copy will be e-mailed to the subject. No subjects will be involved in research activities unless an investigator or a designated study staff has obtained documentation of legally effective informed consent of the subject. The collection of protected health information (PHI) and questionnaires are considered to be research activities requiring prior documentation of informed consent.

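### The Aim 1 analysis uses only app sessions, so it cannot answer H1a, which concerns willingness among caregivers screened

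*Combined protocol and SAP*

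**What the plan says.** Section I (Specific Aims, Aim 1) gives hypothesis 1 two parts. H1a reads "We expect 80% of caregivers screened will report willingness to use the mindfulness app". H1b expects at least 75% of participants to complete training, with completion defined as "at least 80% of expected engagements with the app". Section IV (Data Analysis, Aim 1) repeats both parts. It then gives one sentence of analysis, in which "the number of subjects and the number of sessions completed by each will be examined to determine if at least 80% of subjects engage". Engagement here means use of the app, and the same sentence adds a second check, that 75% or more complete a full dose.

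Four other places bear on whether willingness could be measured:

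- **III.C (Screening)** describes an online REDCap eligibility survey covering loneliness and stress, with an option to leave contact details.
- **III.F.1 (phone screen)** says "demographics data will be collected (age, gender, race/ethnicity, education, marital status, living arrangements, caregiver status"), together with short stress, cognition, alcohol and loneliness instruments. Willingness is not listed.
- **III.F.4 (follow-up)** includes an evaluation of the study experience, asked after the intervention.
- **V.A (monitoring plan)** provides for administrative reports of numbers screened, enrolled, completed and discontinued.

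**The concern.** The hypothesis and its analysis share a threshold of 80% but describe different quantities. H1a is about what people say, among everyone screened. The analysis is about what people do, among those who were given an app. A caregiver who was screened and declined has no session count and cannot enter the calculation.

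Feasibility and acceptability make up the first aim of this pilot, and willingness is half of the hypothesis attached to it. If the plan is followed as written, a report could say that hypothesis 1 was supported because enrolled people used the app, even if many of those approached did not want it. It could equally say that hypothesis 1 failed because app use was low, although nearly everyone asked was willing.

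**Working it through.** **Step 1. Set the criteria side by side.**

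| | H1a as stated (Sections I and IV) | First check in the Section IV analysis sentence |
|---|---|---|
| Outcome | Reported willingness | Engagement with the app |
| Denominator | Caregivers screened | Subjects |
| Data used | None named | Session counts |
| Threshold | 80% | At least 80% |

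The analysis sentence does not define its denominator. Taking it as people who received an app is sound, because only they can have completed sessions, and because the same paragraph names caregivers screened when it means that group.

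**Step 2. Look for another source of willingness data.** Willingness appears only in the hypothesis statements. The contents listed for the REDCap survey and the phone screen do not include it. Those lists are not complete, however. Section II.E is headed "Inclusion Criteria (assessed at the HARP screening assessment") and includes caregiver strain, and II.F, with the same place of assessment, covers meditation practice; III.F.1 lists neither. Part of screening also runs under separate HARP protocols. An item may therefore exist, but no stated analysis uses one. The follow-up evaluation comes too late and reaches participants only. The V.A reports give counts, not willingness.

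**Step 3. Show that the two proportions can separate.** The plan's only related arithmetic is its enrolment figure: 50 / (1 − 0.20) = 62.5, rounded up to 63, which reproduces. The documents give no number screened. Assume, for illustration, that only willing caregivers enrol and that there are no other screen failures. The number screened to enrol 63 is then 63 / willingness:

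- 60% willing: 63 / 0.60 = 105
- 70% willing: 63 / 0.70 = 90
- 80% willing: 63 / 0.80 = 78.75, so 79
- 90% willing: 63 / 0.90 = 70

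Engagement among the 63 could be 90% in every row. The engagement check passes each time, while H1a falls short of 80% in the first two rows.

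**Step 4. How the engagement check itself behaves.** The chance that at least 80% of n subjects engage is the binomial tail P(X ≥ r), with r = 0.80n rounded up. The plan does not say whether one arm or both are counted, so n is shown as a range. The values 25 and 32 assume equal allocation of 50 or 63 people.

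| n counted | r | True engagement 75% | True engagement 90% |
|---|---|---|---|
| 25 | 20 | 0.38 | 0.97 |
| 32 | 26 | 0.28 | 0.96 |
| 63 | 51 | 0.17 | 0.99 |

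Willingness appears nowhere in this calculation. The table only illustrates that; the point itself rests on Step 1.

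**The case against.** The strongest reply is that nothing has been replaced. The phrase about 80% and engaging with the app echoes H1b's own definition of completion, so the sentence may be a garbled restatement of H1b. The opening reference to hypothesis 1 covers both parts and does not assign the 80% check to H1a. This stands: a reader might infer that the plan substitutes engagement for willingness, but the text does not settle that. It does not rescue H1a, because on this reading H1a has no analysis at all.

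A reader might also infer that willingness is not collected. The documents do not support that either, since the screening lists are incomplete and the HARP instruments are not shown.

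Third, the probabilities add little. They depend on an unstated denominator, and a rule that omits willingness obviously does not depend on it. H1a is also worded as an expectation of 80%, not as a pass mark. All of this is accepted, which is why the figures are given only as a range.

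Finally, reading the reference to a full dose in the H1b check as a stricter, second definition goes too far. It most naturally refers back to the 80% definition, and III.G allows the session count to be worked out. What remains there is wording.

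**Conclusion.** The point holds in this form: the stated analysis for hypothesis 1 cannot answer H1a, on either reading of the sentence, and no other section supplies an analysis of willingness. This is a mismatch between a hypothesis and its own analysis rule, and it should be fixed.

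Its reach is limited. It affects one of the two parts of the Aim 1 hypothesis, which is descriptive feasibility reporting in a pilot. A reader might extend it to the loneliness and mechanism results, but Aims 2 and 3 have their own models and do not depend on the Aim 1 check. No corrected H1a figure can be computed, because the documents give neither the number screened nor any willingness data. The conclusion comes from comparing the text and does not rest on the illustrative assumptions about numbers screened, engagement rates or allocation.

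**What to change.** Reword the Aim 1 analysis paragraph as follows.

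- **H1a.** Number answering yes to a willingness item, divided by all caregivers asked at one named screening stage, compared with 80% and reported with a 95% CI.
- **Name the stage and whom it leaves out.** The phone screen is a practical choice: caregiver status is recorded there, and III.B says "All eligible participants will be given information about this study at their HARP phone screen assessment". On the online route, however, the REDCap survey comes first, so a phone-screen denominator excludes people who left before it. III.B also promises study information only to those eligible, so anyone else who is to be asked would need it too.
- **If no item exists,** add one yes/no question. This may require a change to the separately approved HARP screening protocol.
- **If screening is closed and no item was used,** state that H1a was not measured. Report uptake, meaning enrolled divided by eligible caregivers offered the study, and label it as uptake. Enrolled divided by screened is not a substitute: III.C introduces the survey "given the relatively low base rate of loneliness, which is our key inclusion criteria", so that ratio mixes ineligible people with those who declined.
- **Engagement.** Report it separately, and not as the test of H1a.
- **H1b.** Use its own definition of completion among all participants randomised to mindfulness, against 75%. If all 14 sessions in III.G (10 introductory plus four final) are expected, 0.80 × 14 = 11.2, so 12 or more.

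The cost is one reworded paragraph and possibly one screening question with its approval. The feasibility figure may look less favourable once unwilling caregivers are in the denominator.
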